1A.2: Ascites Info	1B.4: Ascites Info	2A.2: Ascites Info	2B.4: Ascites Info

Subgroups 1 and 2 will involve the presentation of educational materials in text-and-graphic format (Cirrhosis Toolkit), with each subgroup focusing on a single subject or section of the material. Subgroups 3 and 4 will be presented with similar material in video format, also focusing on a single subject per subgroup. Recruitment for this study will conclude once 40 subject-experiments have been completed for each subgroup.

Subjects will be given the option to be randomized into an additional study subgroup (For example: if they were randomized into subgroup 1A.1 in the first round, they would be randomized into 1A.2 or 1B.4 for their second round of participation) and participate in the study a second time. Enrollment will conclude once 160 subject-experiments have been completed for each study arm.

Inclusion Criteria

1. Age 18 years or older
2. Cirrhosis, as diagnosed by imaging, elastography, biopsy, or decompensation
3. Available email address
4. Arm 1: New patient visit for cirrhosis (and diagnosis within the last 6 months)
5. Arm 2: Previous cirrhosis diagnosis (>6 months)

Screening

For Arm 1, patients with a new diagnosis of cirrhosis will be identified by reviewing the University of Michigan Hepatology Clinic outpatient schedule and related notes in the Electronic Medical Record.

For Arm 2, Patients with >6 months history of cirrhosis diagnosis will be identified via Datadirect, previously established patient lists, and the University of Michigan Hepatology Clinic outpatient schedule.

Patients who meet the inclusion criteria will be randomized into one of the above subgroups and sent an email invitation to participate in the study. Potential participants will not be called or approached in person. The study invitation message will include contact information for study staff members in case these patients have any questions or would like to discuss the study in more detail before proceeding.

Procedures

The study will be conducted completely online, via REDCap. The initial study invitation email will include a link to the REDCap database, where participants will complete study questionnaires and activities. Informed consent for this study will be conducted online via REDCap.

Demographics Survey

Participants will be asked to report their age, sex, cause of cirrhosis, and any history of ascites, variceal bleeding, or HE.

Pre-Evaluation

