Based on their randomly assigned subgroup, participants will complete a Pre-Evaluation, consisting of 5-6 content-specific questions, to determine each participants' baseline level of content knowledge. Pre-Evaluation scores will be recorded, but not presented to participants.

Educational Intervention

Participants will be prompted to review the educational material associated with their assigned subgroup. This will involve reading a specific section of the Cirrhosis Toolkit or watching videos. Participants will be given unlimited time to review and interact with educational materials and will be prompted to complete the Post-Evaluation when ready.

Post-Evaluation

Participants will be directed to respond to a set of content-specific questions identical to the Pre-Evaluation they completed earlier in the study, but in a randomized order. Post-Evaluation scores will be presented to participants after they complete the optional feedback survey (below).

The change in score between pre-and-post-evaluations for each participant will inform the results of aims 1 and 2. For questions with multiple correct answers, no partial credit will be awarded.

Debrief

Participants will be informed that all mandatory study activity has been completed and thanked for their time.

The study debrief will present participants with multiple optional study activities:

- 1) Complete the Feedback Survey
- 2) Contact study staff for further questions
- 3) Review their Post-Evaluation Score and complete a brief survey response
- 4) Re-enroll in the study to 'learn more'

- 1) The Feedback Survey will consist of questions related to aims 3 and 4.

Questions:

- Did you find this material helpful? (Likert scale)
- Would you recommend this material to others? (yes/no)
- Would you prefer further educational materials in text or video format?
- Do you have any suggestions for improving these educational materials? (text box)

- 2) Participants will be given contact information for study staff members if they have any further questions.

3) Participants will have the option to review their post-evaluation scores only after all other activities have been completed, such as the feedback survey. Scores will be reported as [# correct]/[# of questions] Participants will be asked to reflect on their score:

-Are you satisfied with your score? (visual analog scale or Likert)

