-What are your next steps for further education? (select all that apply: Nothing, talk to Hepatologist, talk to Nurse, talk to nutritionist, talk to other medical professional, internet search, talk to family and friends, other (please explain))

4) Participants will be given the option to 'learn more' and re-enroll in the study. If participants elect to re-enroll, they will be randomized into a different subgroup of the same study arm.

Statistical Analysis

Aim 1: Matched pair Wilcoxon comparing pre-test and post-test scores in the whole study population.

Aim 2: Matched pair Wilcoxon comparing score change (from pre to post) between video group and text group.

Aim 3: Descriptive statistics of Likert scale results.

Aim 4: Will report key themes from patient open-ended responses.

Foreseeable Risks and Discomforts

The risks of this study are primarily psychological. Subjects may become frustrated if performing poorly on the pre-or-post-evaluations. Patients may have privacy concerns about study communication via email or conducting study activities online or on their personal device.

Expected Benefits

A potential direct benefit for participants is the opportunity to learn something new about cirrhosis.

Privacy and Confidentiality

Redcap, a secure and HIPAA-compliant electronic program, will be used for all data collection and study activities. Once randomized, participants will be identified only by a study ID number. Results of the testing and any other information provided by the subject are available for analysis under the heading of this number only, not by name or other personally identifiable information. No names or personally identifiable information will be collected or used in any publications.

We will keep a separate password protected screening log on the University shared drive in a secured location. Only study personnel will have access to the electronic screening log that maps the Subject ID number and Screening ID number (if applicable) to the participant's email address. Only limited identifiable data will be collected for screening purposes.

Data and Safety Monitoring

There are no safety concerns in this study. We will store data on a secure U-M server. Study staff will proofread data weekly to verify accuracy. PI will complete a comprehensive review of all data prior to analysis.

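### Aim 2 compares unadjusted score change: the recorded baseline score is only subtracted, which costs precision, and the score scale is not stated

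*Combined protocol and SAP*

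**What the plan says.** The Statistical Analysis section gives Aim 2 one sentence: "Matched pair Wilcoxon comparing score change (from pre to post) between video group and text group". The Post-Evaluation section confirms the outcome: "The change in score between pre-and-post-evaluations for each participant will inform the results of aims 1 and 2". No covariate, regression model or stratification is named anywhere in the document.

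The baseline is available. The Pre-Evaluation section describes a test "consisting of 5-6 content-specific questions, to determine each participants' baseline level of content knowledge" and states: "Pre-Evaluation scores will be recorded, but not presented to participants". On scoring, the Post-Evaluation section adds: "For questions with multiple correct answers, no partial credit will be awarded". The only score format given is number correct over number of questions. It appears in the Debrief section and describes how participants see their post-test result. It does not define the analysis variable, and the plan does not say which topic has five questions and which has six.

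On numbers, the Overview says: "Recruitment for this study will conclude once 40 subject-experiments have been completed for each subgroup". The Debrief section allows repeat participation: "If participants elect to re-enroll, they will be randomized into a different subgroup of the same study arm".

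**The concern.** Subtracting the baseline fixes the pre-to-post slope at 1. On a short bounded test the slope is usually lower, because high scorers have no room to gain and low scorers drift upward on retest. The change score then carries noise that a fitted slope would remove. It also leaves part of any chance baseline difference between formats in the estimate, with the sign reversed.

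Aim 2 is the trial's main randomised comparison, and no power calculation shows that there is precision to spare. Because only a rank test is named, Aim 2 as written yields a test but no video-minus-text difference with an interval.

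Two smaller gaps sit beside this. The analysis scale for sets of different length is undefined, and arm and topic, which define the planned cells, are absent from the analysis.

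**Working it through.** **1. The plan's own figures.** Eight subgroups × 40 = 320 subject-experiments. Four text and four video subgroups give 4 × 40 = 160 per format, so allocation is 1:1. The 320 reproduces as a count. No alpha, power, effect size, SD or correlation is given, so those below are assumptions (two-sided 0.05, 80% power).

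**2. Variances.** Let the pre SD be s, the post SD ks, and the pre-post correlation r.

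- Change score: s²(1 + k² − 2rk)
- Baseline-adjusted: s²k²(1 − r²)
- Change minus adjusted: s²(1 − rk)², which is never negative and is zero only when the slope rk equals 1

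With k = 1 the ratio of adjusted to change-score variance is (1 − r²)/[2(1 − r)] = (1 + r)/2.

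| r | k = 0.8 | k = 1 | k = 1.25 |
|---|---|---|---|
| 0.3 | 0.50 | 0.65 | 0.78 |
| 0.5 | 0.57 | 0.75 | 0.89 |
| 0.7 | 0.63 | 0.85 | 0.98 |

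**3. What this means at 160 per format (k = 1, independent experiments).** The detectable difference in SD units is (1.960 + 0.842) × √(variance × 2/160).

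| r | Change score | Adjusted | 320 adjusted experiments are worth | Adjusted power where change score has 80% |
|---|---|---|---|---|
| 0.3 | 0.371 | 0.299 | 320/0.65 ≈ 492 (54% more) | 93.5% |
| 0.5 | 0.313 | 0.271 | 320/0.75 ≈ 427 (33% more) | 89.9% |
| 0.7 | 0.243 | 0.224 | 320/0.85 ≈ 376 (18% more) | 86.0% |

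**4. Chance imbalance.** The share of a baseline difference left in a change score is rk − 1, which is −0.5 at r = 0.5 and k = 1.

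**5. Simulation on bounded scores (all inputs assumed).** 3,000 trials, eight cells of 40, one row per participant, 5 or 6 items by topic, pre-to-post gain 0.9 logit, format effect 0.35 logit, arm effect 0.3 logit, ability SD 0.6, 1.0 or 2.0.

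| Pre-post correlation, about | 0.28 | 0.49 | 0.74 |
|---|---|---|---|
| Power, rank-sum on raw change | 48.0% | 45.7% | 38.7% |
| Power, change in proportion, unadjusted | 49.9% | 48.2% | 40.3% |
| Power, baseline covariate only | 75.4% | 66.8% | 48.8% |
| Power, baseline plus arm and topic | 75.5% | 66.9% | 48.6% |
| Variance ratio, adjusted to change | 0.56 | 0.65 | 0.79 |

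With no format effect, every method rejected in 4.1% to 5.4% of trials. Once baseline is in the model, arm and topic move power by at most 0.2 points, so almost all the gain comes from the baseline score.

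**6. Scale.** As a proportion, one item is 100/5 = 20 points on a five-question set and 100/6 = 16.7 points on a six-question set; as a count it is 1 on either. In a separate simulation with r about 0.5, a rank-sum test on raw change and on proportion change had power 0.409 versus 0.403 at a 0.3 logit effect, and 0.626 versus 0.613 at 0.4 logit. The choice hardly affects power.

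**The case against.** A prespecified change score is a legitimate outcome. Under randomisation it is unbiased with correct type I error, and the plan states no power target that it would miss. That stands: this is a question of efficiency and not of validity.

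The power of the test as written cannot be computed, because no pairing between video and text participants is defined. That also stands. The figures compare an unpaired change-score analysis with an adjusted one; they do not measure the matched-pair test.

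The size rests on assumptions. The 0.35 logit effect sits where power gaps look wide: at 0.8 logit the three pairs become 98 versus 100, 98 versus 100 and 96 versus 99%, and at 0.1 logit all are about 10 to 13%. The pre and post questions are also identical, so a correct answer will tend to stay correct, which the simulation above does not model. Suppose each item is correct at baseline with probability 0.5 and retained, and 40% of missed items are gained. Per item the pre variance is 0.25, the post variance 0.7 × 0.3 = 0.21, and the covariance 0.5 − 0.5 × 0.7 = 0.15, so r ≈ 0.65. The change variance is 0.25 + 0.21 − 0.30 = 0.16 and the adjusted variance 0.21 − 0.15²/0.25 = 0.12, a ratio of 0.75. A simulation with similar carry-over gave about 0.58 to 0.70. The gain persists, but the 50 versus 75% contrast is toward the favourable end.

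The equivalent sample sizes treat experiments as independent, which repeat participation weakens. The missing effect estimate comes from naming only a rank test, since a change score can supply a mean difference. The scale, arm and topic points would not justify a change by themselves.

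**Conclusion.** The concern holds as a loss of precision in the main randomised comparison, without bias or type I error inflation. With equal SDs and r between 0.3 and 0.7, adjustment removes 15% to 35% of the variance. With the post SD at 0.8 to 1.25 times the pre SD, the reduction runs from about 50% down to 2%. The direction does not depend on these inputs: with 1:1 randomisation and this sample size, fitting the slope is in essence never less precise than fixing it at 1. The size does depend on them, and the documents supply none. The undefined scale is a real but minor ambiguity. If question count follows topic, the equal cells balance it across formats, so it affects weighting and reporting rather than bias. Leaving out arm and topic has almost no effect on precision when the cells are balanced.

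**What to change.** Make the primary Aim 2 analysis a linear model of Post-Evaluation proportion correct on format (video versus text), with Pre-Evaluation proportion correct, study arm and topic as covariates. Use one row per completed subject-experiment and robust standard errors clustered on participant, since a participant may contribute a second row. Report the adjusted video-minus-text difference with its 95% CI, and state that all scores are analysed as proportion correct. This model replaces the matched-pair test.

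As a sensitivity analysis, use an unpaired rank-sum test on change in proportion correct, stratified by arm and topic, with first participations only. Estimates by arm and by topic are optional and should be labelled exploratory.

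The cost is SAP wording and slightly more analysis. Every variable is already collected. The change should be made before the data are examined.
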